9.4.2 Safety Data

Adverse Event Data

Safety data will be summarized for the safety evaluable population. These data will include AEs and laboratory parameters. AE terms will be coded using the Medical Dictionary for Drug Regulatory Activities (MedDRA; version 16.0 or higher). AEs will be summarized by body system, preferred term, severity and relationship to treatment. SAEs, deaths and AEs leading to early discontinuation of study drug will be summarized. DLTs will be provided in a separate listing by dose. Laboratory parameters will be summarized by maximum NCI CTCAE severity grade and also by change from study entry to scheduled time points using descriptive statistics. Laboratory parameter listings will

include the normal ranges for each parameter. Each value will be classified as falling above, below or within the normal range.

Data summaries will include only treatment-emergent AEs (TEAEs), defined as events occurring on or after Day 1 Cycle 1 up to and including 30 days after last dose.

Pharmacokinetic versus ECG Parameters

The relationship between changes in ECG parameters and plasma concentration of APR-246 will be explored where possible using non-linear mixed effects modelling.

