3.2 Sub-Study Objectives and Endpoints

Sub-study Objectives: Same as Main Study Objectives, except safety and tolerability, in addition to preliminary efficacy, are Primary Objectives.

Sub-study Primary Endpoint for safety and tolerability: The safety profile (adverse events [AEs], laboratory assessments, physical findings and biomarkers) of APR 246 with a shorter infusion and PLD chemotherapy.

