6.5.4 Cardiac Safety Monitoring in Relation to Treatment With PLD

Whenever cardiomyopathy is suspected, i.e., the LVEF has substantially decreased relative to pretreatment values and/or LVEF is lower than a prognostically relevant value (e.g., < 45%), the benefit of continued therapy must be carefully evaluated against the risk of developing irreversible cardiac damage. Cardiology consultation is recommended. Local practice should be followed.

Previous clinical trial experience with PLD for the treatment of ovarian cancer has been summarized and may be a useful reference [18].

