7.3.4 Recording of Adverse Events

7.3.4.1 Time Period for Collection of Adverse Events

AEs will be collected throughout the study, from informed consent until 30 days after the last administration of study treatment.

SAEs occurring in this period should be reported to the Theradex[®] Safety Desk in the usual manner (see Section 7.3.5).

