7.3.4.2 Follow-up of Unresolved Adverse Events

All AEs should be followed until they are resolved or until the EOT visit, whichever comes first. All AEs that are still ongoing after the EOT visit, should be followed on a regular basis, according to the investigator's clinical judgment, until the event has resolved or until the investigator assesses it as chronic and all queries have been resolved. After the EOT visit, AEs that are unrelated to APR-246 (serious or non-serious) or related but not serious, do not require further recording in the eCRF. For Related SAEs that resolve, the date the event resolved and the outcome of Resolved or Resolved with sequelae, as appropriate, should be recorded on the eCRF and the SAE Report Form. The Sponsor retains the right to request additional information for any patient with ongoing AE(s) at the end of the study, if judged necessary.

If an Investigator learns of any SAEs, including death, at any time following 30 days after the last administration of study treatment and he/she considers there is a reasonable possibility that the SAE is related to the study treatment, the Investigator should notify Theradex[®] Safety Desk.

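### Section 9.4.2 leaves related SAEs with onset more than 30 days after last dose out of the AE, SAE and relationship summaries, and does not settle the scope of the death summary

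*Combined protocol and SAP*

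**What the plan says.** Section 9.4.2 plans AE tables by body system, preferred term, severity and relationship to treatment. It adds that "SAEs, deaths and AEs leading to early discontinuation of study drug will be summarized", and that sentence carries no time window. The AE part of the section then closes with a restriction on its summaries: they "will include only treatment-emergent AEs (TEAEs), defined as events occurring on or after Day 1 Cycle 1 up to and including 30 days", counted from the last dose. It makes no exception for related events.

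The collection and reporting rules are in Section 7.3:

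- Section 7.3.4.1 sets the routine window: "AEs will be collected throughout the study, from informed consent until 30 days after the last administration of study treatment".
- Section 7.3.4.2 reaches past it. It covers "any SAEs, including death, at any time following 30 days after the last administration of study treatment", on the condition that the investigator "considers there is a reasonable possibility that the SAE is related to the study treatment, the Investigator should notify" the Safety Desk.
- Section 7.3.5 says that all SAEs go into the eCRF and gives no cut-off date.
- Section 7.3.4.10 has deaths in the study or its follow-up period reported. Deaths unequivocally due to progression are documented in the eCRF but not reported as SAEs.

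Section 9.2 states that all patient data, safety included, will be summarized and listed in full, and that a SAP will add detail before data lock.

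**The concern.** The plan asks sites for late SAEs that an investigator has judged possibly related and, read literally, enters them in the trial database. It then has a summary rule that shuts them out of the tables where a reader looks for related serious toxicity. A listing keeps the event visible, but the event does not enter any reported count or rate.

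The safety profile is a secondary endpoint of the Main Study (Section 3.1.4). In the Sub-Study it is primary: "Sub-study Primary Endpoint for safety and tolerability: The safety profile" of the shorter infusion with PLD (Section 3.2). Patients remain under observation after treatment, with visits at least every 8 weeks (Section 7.2.6) and survival checks every 6 months after progression (Section 7.2.7), so a late event can come to light. When one does, the plan gives two instructions: Section 9.2 says to summarize it and Section 9.4.2 says not to.

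**Working it through.** The plan states no figure to reproduce on this point. The check is a comparison of texts, followed by a simple illustration of size. Day 30 below means 30 days after last dose.

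**Step 1. Follow one event through the rules.** Take an SAE with onset on Day 40 that the investigator considers related.

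- Notified? Yes, if the investigator learns of it (Section 7.3.4.2).
- In the eCRF? Yes on a literal reading of Section 7.3.5.
- A TEAE under Section 9.4.2? No, because Day 40 is after Day 30.
- In the AE, SAE and relationship-to-treatment summaries? No, because these include only TEAEs.
- In a listing? Yes, under the full-listing rule of Section 9.2.
- Summarized under Section 9.2? Yes by its words, which is where the two sections conflict.

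The planned SAP does not resolve this by itself. Section 9.2 describes it as expanding on the analyses set out in Section 9, so by default it inherits the restriction.

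**Step 2. Follow a late death.** Section 9.4.2 promises a death summary without a window, and its restriction is worded for adverse events. Section 7.3.4.10 keeps progression deaths out of the SAEs, so a death summary built from TEAEs alone would omit them even within 30 days. Either the death summary covers all recorded deaths, or it covers only deaths attached to a TEAE. The text supports no firm choice.

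**Step 3. Check the edge of the window.** Section 7.2.5 places the end-of-treatment visit at 30 +/- 2 days after the last APR-246 dose, that is Day 28 to Day 32. If that dose is also the last study treatment, a related SAE that starts on Day 31 or 32 and is found at an on-time visit falls outside the summaries.

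**Step 4. Illustrate the size.** For k patients whose only related SAE starts after Day 30, the related-SAE rate falls by k/N. The sample sizes in Section 9.1 are 25 per part, or 25 + 25 = 50 pooled. I assume that the number treated equals these figures.

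- k = 1: 1/25 = 4.0 percentage points in one part; 1/50 = 2.0 points pooled.
- k = 2: 2/25 = 8.0 points in one part; 2/50 = 4.0 points pooled.
- If the Sub-Study stops after its first stage of 14, k = 1 gives 1/14 = 7.1 points.

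The documents give no expected value of k, and zero is possible. A patient who also had a related SAE within the window is already counted, so for that patient the incidence does not change.

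**The case against.** The strongest reply is that the summary window matches the collection window. Routine AE collection stops at 30 days (Section 7.3.4.1), and Section 7.2.6 lists tumor assessment, CA-125 and biomarker samples at follow-up visits but no AE review. After Day 30 the plan relies on an investigator who happens to learn of an SAE and judges it related. Adding such events to the same numerator would mix active and passive ascertainment. This stands. The 30-day rate is valid for its own window and should not be altered. It is a reason to show late events separately, not to leave them out of every AE and SAE table.

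It is also fair that late events are not lost, since Section 9.2 requires full listing, and that no decision rule depends on the TEAE window. The Sub-Study safety gate uses DLTs in the first 6 patients (Section 9.1), DLTs have their own listing (Section 9.4.2), and the Safety Review Committee sees safety data directly (Section 1.5). These facts limit the consequence to reporting.

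A reader might infer more than the text allows, in four ways:

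- *Late deaths are excluded from every death summary.* Step 2 shows ambiguity, not exclusion. A late death from an AE that began within the window may still be counted under that AE, and a death without prior progression is a PFS event (Section 9.4.1).
- *Sites are bound to report every late SAE.* Section 7.3.4.2 covers only SAEs the investigator learns of and considers related, and it says the investigator should notify.
- *The reported rates are biased.* That treats a rate for a stated window as if it were a rate over all follow-up.
- *Late PLD cardiotoxicity will be missed.* Section 6.5.4 mentions "the risk of developing irreversible cardiac damage" when weighing continued therapy. It says nothing about onset after Day 30, so it can serve only as an example of the kind of event that might matter.

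**Conclusion.** The point holds in a narrow form. Section 9.4.2 states a rule, and under it related SAEs with onset after Day 30 are left out of the AE, SAE and relationship-to-treatment summaries although Sections 7.3.4.2 and 7.3.5 ask for them to be notified and recorded. Section 9.2 points the other way. Whether the death summary shares the 30-day limit is undefined.

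The size is unknown. Each affected patient with no earlier related SAE is worth 4 points in a part of 25 treated patients or 2 points in 50, and omission can lower the count of related events but never raise it. This rests on those assumed denominators and on reading the eCRF rule in Section 7.3.5 as having no time limit. Neither the response-rate test nor any stopping rule is affected. It should be corrected because safety is a Sub-Study primary endpoint and the correction is cheap.

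**What to change.** Keep the 30-day TEAE window for the main incidence tables. Add to Section 9.4.2, and carry into the SAP, two statements:

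1. SAEs with onset more than 30 days after last dose and assessed as related to study treatment are summarized on a separate line of the SAE and relationship tables, labelled as passively reported.
2. The death summary covers all recorded deaths, split into within 30 days of last dose and later, with cause.

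This removes the conflict with Section 9.2 and leaves the 30-day rates intact. The cost is a short text change and one extra line in each affected table. No new data collection is needed, because late related SAEs are already to be notified and recorded and deaths are already documented. The downsides are that reported related-event counts may be slightly less favorable, and that the late line rests on less complete ascertainment, which the label makes plain.

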9.4.3 Pharmacokinetic data

APR-246 concentrations will be determined by a validated HPLC tandem mass spectrometry (LC/MS/MS) method. The sampling scheme is designed to allow evaluation by non-compartmental as well as population pharmacokinetic analysis. The decision on the method and whether or not the APR-246 pharmacokinetic evaluation and reporting will be done as standalone or pooled across several clinical studies with APR-246 will be taken at the time of analysis. PK parameters of APR-246 will include: Cl, V_{ss}, C_{max}, AUC₀₋₂₄, AUC_{0-∞} and t_{1/2}.

Individual and mean profiles of concentrations of all analytes (APR-246) will be presented graphically. Protocol-specified blood sampling times will be used in the graphical presentation.

No formal statistical analysis beyond descriptive statistics is planned. For each PK parameter, individual and mean data and summary statistics (including number of subjects, arithmetic mean, geometric mean, SD, CV, median, Min and Max) will be presented.

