6.3 Main Study Treatment Administration

Starting within 28 days of registration, patients will receive a fixed dose of 4.5 g APR-246 (1.5 g of the dose during first 45 minutes followed by 3 g of the dose during 5 hours 15 minutes) on Days 1 to 4 with PLD 40 mg/m² on Day 4 (Figure 3). The PLD administration to be given on Day 4 only should commence 2 hours after the start of the APR-246 infusion.

Similarly for the following 28-day cycles, APR-246 will be administered on Days 1 to 4 with the PLD infusion on Day 4 starting 2 hours after the start of the APR-246 infusion.

Figure 3. Treatment Administration

Note: The entire dose should be given even if the infusion needs to be extended beyond a total time of 6 hours (e.g. due to slightly larger start volume in prefilled infusion bags).

APR-246 Treatment Duration

Treatment will be repeated every 28 days in the absence of disease progression or unacceptable toxicity. Supportive therapy, including growth factors, can be given as per institutional standard of care.

Pegylated Liposomal Doxorubicin Dosing

[figure not shown]
The dose of PLD will be calculated based on the body surface of the patients at 40 mg/m² as per standard practice at that hospital.

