6.5.2 Sub-Study APR-246 Dose Reductions

After an adverse event considered as related, the infusion time may be extended to a total of 4 hours to achieve a reduced maximum blood concentration of APR-246. If a related adverse event occurs with the 4 hour infusion, APR-246 dose will be de-escalated. Dose reductions are defined in Table 2. If there is a further need for a patient to have another dose reduction, this should be discussed with the Sponsor prior to any treatment decisions. The type, severity and duration of the symptoms, adverse event and infusion timings (start and stop) should be carefully documented in the patient’s medical charts as per trial procedures.

Table 2. Dose Modifications of APR-246 in Sub-Study

Dose Modification	APR-246 Dose and Regimen
Starting Regimen, 3-hour infusion	APR-246 4.5 g 2.3 g (for first 45 minutes) + 2.2 g (for 2 hours 15minutes)
4-hour infusion	APR-246 4.5 g 2.0 g (for first 45 minutes) + 2.5 (for 3 hours 15 minutes)
4-hour infusion of reduced amount*	APR-246 3.7 g 1.6 g (for first 45 minutes) + 2.1 g (for 3 hours 15 minutes)

* Discuss with Sponsor and or medical monitor before implementing this reduction.

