8.4.1 APR-246

A full PK profile will be taken during Cycle 1 from patients selected for ECG Holter testing (Table 8), followed by sparse PK sampling from Cycle 2 onwards (Table 9).

For all other patients, sparse PK sampling will be done from Cycle 1 until the last Cycle (Table 9).

The objective of the sparse PK sampling scheme is to enable construction of individual PK parameters (AUC and C_{max}) for correlation with efficacy and safety. The PK of APR-246 follow a bi-exponential decline and therefore a minimum of three samples are needed to construct the PK individual profiles.

The PK sampling scheme allows for some flexibility in the timing of the blood sampling and whenever possible time windows for sample collection are given. Nevertheless it is critical for the PK evaluation that the exact times of dose administration and PK sample collection are recorded on each occasion.

Table 8. PK Blood Sampling Time Points for APR-246 During Cycle 1 (Patients Selected for ECG Holter)

Day 1	Before infusion	0-2 hrs prior to APR-246 infusion
	During infusion	5-15 min prior to end of infusion
	After infusion	15 mins +/-3 min AFTER the end of infusion
		1 hr +/-5 min AFTER the end of infusion
		3 hrs +/-15 min AFTER the end of infusion
Day 2	Before infusion	0-30 min prior to APR-246 infusion
Day 4	Before infusion	0-30 min prior to APR-246 infusion
	During infusion	5-15 min prior to end of infusion
	After infusion	15 min +/-3 min AFTER the end of infusion
		1 hrs +/-5 min AFTER the end of infusion
		3 hrs +/-15 min AFTER the end of infusion
Day 5	No infusion	12-24 hrs AFTER the end of Day 4 infusion

Table 9. Sparse PK Blood Sampling Time Points for APR-246

D1 C1*-final cycle	Before infusion	0-2 hrs prior to APR-246 infusion
	At end of infusion	+/-5 min relative to the end of infusion
	After infusion	30-60 min AFTER infusion
D4 C1*-final cycle	Before infusion	0-2 hrs prior to APR-246 infusion
	At end of infusion	+/-5 min relative to the end of infusion
	After infusion	30-60 min AFTER infusion

*From Cycle 2 (C2) in patients selected for ECG Holter testing.

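### Section 9.4.3 says the PK sampling supports non-compartmental analysis, but no sample is taken between pre-dose and the last minutes of a front-loaded infusion, so AUC would be too low and CL too high

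*Combined protocol and SAP*

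**What the plan says.** Section 9.4.3 says of the blood samples: "The sampling scheme is designed to allow evaluation by non-compartmental as well as population pharmacokinetic analysis". The decision on method "will be taken at the time of analysis". The parameters to report include Cl, Vss, Cmax, AUC0-24, AUC0-∞ and t1/2, with descriptive statistics only.

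The infusion has a fast and a slow step. Section 6.3 gives the 6-hour regimen as "1.5 g of the dose during first 45 minutes followed by 3 g of the dose during 5 hours 15 minutes". Table 2 in section 6.5.2 gives the 3-hour regimen as "2.3 g (for first 45 minutes) + 2.2 g (for 2 hours 15minutes", and the 4-hour 4.5 g regimen as 2.0 g in 45 minutes followed by 2.5 g over 3 h 15 min.

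The sampling times are in section 8.4.1. Table 8 (full profile, Cycle 1, Holter patients) has a Day 1 pre-dose sample "0-2 hrs prior to APR-246 infusion". The only sample during the infusion is "5-15 min prior to end of infusion", and the next is "15 mins +/-3 min AFTER the end of infusion", followed by 1 h, 3 h and the next morning. Table 9 (all other patients, and later cycles) goes from pre-dose to within "5 min relative to the end of infusion" either side, and then to 30-60 minutes afterwards.

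**The concern.** Non-compartmental analysis knows only the sampled points. Between pre-dose and the end of infusion it draws one straight line. The true curve climbs steeply for 45 minutes and then flattens or falls, so it lies above that line. AUC comes out too low, and CL, which is dose divided by AUC, too high. Sample times are tied to the end of infusion, so the unsampled stretch is longest for the 6-hour regimen and shortest for the 3-hour one.

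Two things are at stake. First, AUC and CL would be reported with an error that differs by regimen, in a study that explores infusion time. Section 8.4.1 also wants individual AUC and Cmax for correlation with efficacy and safety. Second, any peak at the end of the load is never observed, although section 6.5.2 lengthens the infusion in order to lower the maximum concentration.

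**Working it through.** **Inputs from the protocol.** Dose splits are from section 6.3 and Table 2; sample times are from Table 8. Load rate = load / 0.75 h. Later rate = remainder / (T - 0.75 h).

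**Inputs assumed.** The documents show no APR-246 half-life, clearance or volume (sections 2.5.3 and 2.7.1 and Appendix III are redacted). I take a linear one-compartment model with half-life 2, 4 and 8 h, and set CL = 1, since percentage errors do not depend on it. Samples fall at 0, T - 10 min, T + 15 min, T + 1 h, T + 3 h and 24 h. The AUC rule is linear when rising and logarithmic when falling.

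**Worked example: 6 h, half-life 4 h (k = ln 2 / 4 = 0.1733 per h).**
- End of load: C(0.75) = 2.00 × (1 - e^(-0.13)) = 0.2437.
- At T - 10 min = 5.833 h: e^(-0.1733 × 5.083) = 0.4143, so C = 0.2437 × 0.4143 + 0.5714 × 0.5857 = 0.4356.
- Trapezoid from 0 to 5.833 h: 5.833 × 0.4356 / 2 = 1.271.
- True area by mass balance, (amount infused - amount still in the body) / CL: infused = 1.5 + 0.5714 × 5.083 = 4.405; in the body = 0.4356 / 0.1733 = 2.514; difference = 1.891.
- Shortfall: 1.891 - 1.271 = 0.620. True AUC0-24 is 4.388, so the shortfall is 14.1% of it. The later segments are almost exact; the total error is -14.2%.

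The same steps for 3 h give a trapezoid of 0.789 against a true 1.124. The shortfall of 0.335 is 7.6% of 4.414, and the total error is -7.7%.

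**Results: error in Table 8 AUC0-24, Day 1.**

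| 4.5 g regimen | Load share of dose | Load rate, g/h | Later rate, g/h | Half-life 2 h | 4 h | 8 h |
|---|---|---|---|---|---|---|
| 6 h | 1.5/4.5 = 33% | 2.00 | 0.57 | -26.8% | -14.2% | -7.7% |
| 4 h | 2.0/4.5 = 44% | 2.67 | 0.77 | -21.0% | -10.5% | -5.6% |
| 3 h | 2.3/4.5 = 51% | 3.07 | 0.98 | -15.9% | -7.7% | -4.1% |

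- **CL.** At half-life 4 h, AUC0-∞ is off by -13.8% / -10.3% / -7.5% and CL by +16.0% / +11.5% / +8.1% for 6 / 4 / 3 h. With identical true clearance, CL at 6 h would look 1.160 / 1.081 = 1.07 times that at 3 h.
- **Wider assumptions.** With half-life 1-12 h, plus five two-compartment sets (terminal half-life about 2.7-7.1 h), AUC0-∞ error is -4% to -42% (6 h), -3% to -37% (4 h) and -2% to -31% (3 h). The sign, and the order 6 h > 4 h > 3 h, held in every linear Table 8 case.
- **Cmax.** In some of these models the peak falls at 45 minutes, and sampled Cmax is then too low, by up to about 29%.
- **Table 9.** With two-compartment kinetics, extrapolating from two points within an hour of the end of infusion gives AUC0-∞ errors of -34% to -48%. These are not ordered by infusion length in the same way.

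**Check on linearity.** Section 6.5.1 says that 11.1% and 22.2% dose cuts lower average Cmax by 19.4% and 33.4%. Table 1 scales both steps almost in proportion: 1.33/1.5 = 0.887 and 2.67/3 = 0.890; 1.16/1.5 = 0.773 and 2.34/3 = 0.780. Linear kinetics would therefore give falls of about 11% and 22-23%. The stated falls are larger, as saturable clearance would produce. In illustrative runs with saturable clearance (assumed parameters), Table 8 AUC0-24 was still too low for every regimen, by roughly 19% to 49%. The true 3 h/6 h AUC ratio was itself about 1.2-1.5.

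**The case against.** The strongest reply is that the plan already has a sound route. Section 9.4.3 keeps population PK open, and section 8.4.1 calls recording of exact dose and sample times critical. Appendix III is by its title a population PK analysis, and section 9.2 promises a further SAP. A model given the actual infusion rates and times does not carry this trapezoidal error. That stands, and it makes the problem conditional on choosing non-compartmental analysis. It does not rescue the statement that the scheme supports both methods.

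Second, a reader might infer that any AUC difference between the 3-hour and 6-hour regimens would be pure sampling artefact, since equal doses should give equal AUC. The documents do not support that. It holds only under linear kinetics, which the Cmax figures in section 6.5.1 put in doubt. The same limit applies to reading the Day 1 concentration at 45 minutes as 53% higher with 3 h than with 6 h (2.3/1.5). Nor is infusion time the only thing that differs between the 4.5 g regimens: the load is 1.5, 2.0 or 2.3 g.

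Third, a reader might infer that the Sub-Study's conclusions are compromised. They are not. Section 9.1 names safety as its endpoint of interest, regimens change on DLTs (section 6.4.1), and no formal PK comparison is planned.

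Finally, Table 8 does have a sample labelled as during infusion, but only in the last 5-15 minutes. On Day 4 the straight line starts from a measured pre-dose value rather than zero.

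**Conclusion.** The statement in 9.4.3 is not correct for AUC and CL. With a third to a half of the dose infused in 45 minutes and no sample until the last minutes, a trapezoidal AUC is too low and CL too high. Under linear models the error grows with infusion length: for an assumed half-life of 2-8 h, Table 8 AUC0-24 is off by about -27% to -8% at 6 h, -21% to -6% at 4 h and -16% to -4% at 3 h. Confidence is high in the direction. The size is not known, because it rests on assumed kinetics. If clearance is non-linear, true AUC may also differ by infusion time, and non-compartmental analysis could not tell that from the sampling error. Severity is low to moderate: PK is a descriptive secondary endpoint, the fault arises only if non-compartmental analysis is chosen, and no decision rule shown uses the result.

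**What to change.** In section 9.4.3, and in the SAP to follow:

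- Name population or compartmental PK as the method for CL, Vss, AUC and Cmax, using the actual two-rate infusion input and the recorded dose and sample times, with a test for non-linear clearance.
- Delete the statement that the scheme supports non-compartmental AUC and CL.
- Report any sampled Cmax as the observed concentration near the end of infusion.

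The cost is a change of wording and modest extra modelling work.

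Optional: in Table 8, re-time one existing sample on Day 1 and Day 4, such as the one 15 minutes after infusion, to the end of the 45-minute step. The number of samples does not change. In the linear models this brought the AUC0-24 error to between -2% and +7%; under saturable clearance errors of up to about -13% remained. It loses an early post-infusion point for a drug that section 8.4.1 describes as bi-exponential, and it leaves Table 9 unchanged. It therefore does not replace the change of method.
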